7.4. Removal of Subjects from the Study

Subjects have the right to withdraw from the study at any time for any reason, including personal reasons. A subject can withdraw without giving a reason. The Investigator should however try to determine why a subject withdraws from the study and document the reason for withdrawal in the source documents and in the EDC system.

Subjects may be withdrawn from the study in the event of:

- Meeting any of the halting rules in Section 7.3
- A severe AE or SAE;
- Difficulties in obtaining blood or other samples;
- Failure of the subject to comply with the protocol requirements or to cooperate with the Investigator.

Subjects must be withdrawn from the study in the event of:

- Withdrawal of consent
- Lost to follow-up
- Death
- Termination of the study by the Sponsor (described in Section 7.2)
- For safety reasons, it being in the best interest of the subject that he/she be withdrawn, in the Investigator's opinion;
- A positive pregnancy test (the subject or, if reported by a male subject, his female partner), or if the subject/partner is non-compliant with the contraception requirements (see Section 4.1);
- Lab confirmed infection with SARS-CoV-2
- Development of a medical condition that requires concomitant treatment with a prohibited therapy (see Section 5.9.2);
- Breaking of the randomization code during administration of the study drug. If the code is broken for safety reporting purposes, the subject may remain in the study; however, in such cases subject and site staff will remain blinded to IP treatment.

The monitor and Sponsor will be informed in the event of a subject being withdrawn from the study. In case of withdrawal due to an SAE (for details on AE reporting see Section 9.5), the Sponsor should be notified within 24 hours; in case of withdrawal for other reasons; the Sponsor should be notified within 2 days from the event.

Subjects who are withdrawn from the study prior to completion of the scheduled study procedures for any reason (AE, withdrawal of consent, etc.) should be contacted by phone for a safety follow-up 4 weeks after vaccination. In case of an AE, the appropriate follow-up will be done.

Subjects who are withdrawn from the study will not be replaced.

8. STATISTICAL METHODS

The Statistical Analysis Plan (SAP), including table shells will be finalized prior to database lock. The final analysis will be completed after the last subject has had Visit 05 (28 days following the QIV dose) and the data base has been locked.

Analyses will be done using SAS software version 9.4 or higher.

Early reviews may be conducted on an expedited basis and included in an interim report, to aid in decision-making for future studies.

- Early reviews prior to database lock will be done on "snapshots" of the data available at the time of analysis. These snapshots will be stored as a permanent record of the trial.
- These reviews will not affect the conduct of this trial.
- Results will be presented by group; reports will display no subject level data.
- Personnel conducting immune response assays and conducting procedures or assessments of subjects will not have access to any data that would unblind them to individual subject treatment codes.

The SAP will elaborate on the analyses described here and will define which analyses would be included in an expedited report.

8.1. Analysis Datasets

The safety set will include any subject who receives administration of IP.

The full analysis set (FAS) will include all subjects randomized, received IP and had at least one post baseline assessment.

A per protocol set (PPS) may also be evaluated, which will include all subjects in the FAS with no major protocol violations or deviations.

8.2. Subject Disposition and Baseline Characteristics

8.2.1. Sample size

The sample size of 15 subjects per cohorts 1 and 2, and 90 subjects per cohort 3 were chosen based on reports of studies of other vaccines in early-stage development. This study is not powered for any formal comparisons. See Section 1.4 for probability of detecting an AE. Subject Characteristics Data Set

Demographics will include by-treatment summaries of age, height, weight, body mass index (BMI), race, ethnicity, and gender.

Other baseline characteristics may be summarized.

8.3. Safety Analyses

Safety and tolerability of the Sing2016 M2SR influenza vaccine alone and when followed by a licensed vaccine as assessed by Investigator review of subject eDiaries, solicited and unsolicited AEs, treatment-related AEs, SAEs, vital signs, and physical examinations.

AEs will be collected for a period of 28 days following the IP and the QIV doses. However, solicited AEs will be collected by eDiary only after IP administration and not after the licensed vaccine administration. It is therefore anticipated that the summary of AEs post-IP and post-QIV will be different.

8.3.1. Exposure

Vaccine exposure will be summarized by actual dose, percent of expected dose, and percent of subjects receiving the expected dose.

8.3.2. Adverse Events

Treatment-emergent AEs (local and systemic) will be summarized as N (%) with AEs, with related-AEs, and by worst severity.

Incidence of treatment-emergent adverse events (TEAEs) will be reported by MedDRA-coded system organ class (SOC), preferred term (PT), and maximum severity.

Incidence of most frequent TEAEs and most frequent treatment-related TEAEs will be reported by SOC and PT

Listings of subjects who died, discontinued the study due to an AE, or experienced an SAE will be provided.

Dose-site reactions will be presented by reaction and severity.

Post-administration symptoms (eDiary) will be summarized by time point, worst occurrence, and days with symptoms.

8.3.3. Vital Signs

Vital sign results and change from baseline results will be summarized by timepoint using descriptive statistics.

8.3.4. Physical Examination

Abnormal findings of clinical significance in the physical examination will be listed.

8.4. Immunogenicity

Serum antibody, mucosal antibody response will be summarized using descriptive statistics by sampling timepoint for all subjects and by baseline values.

Seroconversion rates will be presented by timepoint and by baseline starting values.

8.5. Appropriateness of Measurements

The assessments which will be made in this study are standard, and are generally recognized as reliable, accurate, and relevant.

9. ADVERSE EVENT REPORTING

9.1. **Definitions**

Adverse Event

An AE is any untoward medical occurrence in a clinical study subject administered a medicinal (investigational or non-investigational) product. An AE does not necessarily have a causal relationship with the treatment. An AE can therefore be any unfavorable and unintended sign (including an abnormal finding), symptom, or disease temporally associated with the use of a medicinal (investigational or non-investigational) product, and whether related to that medicinal (investigational or non-investigational) product.

This includes any occurrence that is new in onset or aggravated in severity or frequency from the baseline condition, or abnormal result of diagnostic procedures, including clinical laboratory test abnormalities.

AEs will be monitored from the time of consent until Visit 03 (Day 28 after the IP dose administration) and from Visit 04 until Visit 05 (Day 28 after the QIV dose administration). SAEs or medically attended events will be documented from the time of consent until Visit 05.

Serious Adverse Event

An SAE is any untoward medical occurrence that meets any of the following conditions:

- results in death;
- is life-threatening, i.e., the subject was at risk of death at the time of the event (e.g., ventricular fibrillation and anaphylaxis). The term does not refer to an event which hypothetically might have caused death if it were more severe.
- requires inpatient hospitalization or prolongation of existing inpatient hospitalization:
 - Hospitalization refers to an overnight admission into hospital for the purpose of investigating and/or treating the AE. Hospitalization for an elective procedure, or routinely scheduled treatment for a pre-existing condition that has not worsened, is not an SAE.
- results in persistent or significant disability/incapacity, i.e., causing substantial disruption of the subject's ability to conduct normal life;
- is a congenital anomaly/birth defect;
- is medically significant, i.e., may not be immediately life-threatening or result in death or hospitalization but may jeopardize the subject's health or may require intervention to prevent one of the above outcomes. Examples of such events are intensive treatment in an emergency room or at home for allergic bronchospasm, blood dyscrasias, or convulsions that do not result in hospitalization or development of drug dependency or drug abuse.

Unlisted (Unexpected) Adverse Event

An AE is considered unlisted if the nature or severity is not consistent with the applicable product reference safety information (FluGen IB).

Suspected Unexpected Serious Adverse Reactions (SUSARs)

A SUSAR is an unexpected serious adverse reaction to the IP.

The Sponsor is to determine if the event is unexpected or not and if unexpected and to report the SUSAR to the Lead PI and FDA. The Lead PI will report any SUSAR(s) to the central IRB. For death and life-threatening cases, reporting should be done within 7 days and follow-up information with details provided within an additional 8 days. All other SUSARs have to be reported within 15 days.

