2.2. Endpoints

2.2.1. Primary Endpoints

The primary endpoints are:

- The number and percentage of study participants who experience solicited local and systemic reactions during the 7 days after administration of investigational M2SR vaccine or placebo, as recorded through subject electronic diary (eDiary).
- The number and percentage of study participants who experience unsolicited AEs during the 28 days after administration of investigational M2SR vaccine or placebo and prior to administration of licensed QIV.
- The number and percentage of study participants who experience SAEs from the time of informed consent through 28 days after receipt of QIV.

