2.2.2. Secondary Endpoints

The secondary endpoints are:

- The number and percentage of study participants who experience unsolicited AEs during the 28 days after administration of licensed QIV.
- The number and percentage of study participants who after administration of Sing2016 M2SR or placebo and before administration of QIV demonstrate:
 - Influenza-specific serum antibody responses measured in MN and hemagglutination inhibition (HAI) assays at specified time points.
 - Influenza-specific mucosal immunoglobulin A (IgA) antibody responses measured in enzyme-linked immunosorbent assay (ELISA) assays at specified time points.

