SAEs occurring at any time during the study will be recorded. Administration site and solicited AEs will be recorded through 7 days after IP vaccination (Day 8). Unsolicited AEs will be recorded from time of consent through 28 days after both M2SR and QIV vaccinations.

While safety and tolerability are the primary objectives, this clinical study is also designed to assess the immune response to one dose of the investigational vaccine and after subsequent immunization with QIV. Immunogenicity will be assessed by measuring serum antibody responses by MN and/or HAI assay and mucosal antibody titers by ELISA. Additional immune parameters will be assessed including T-cell responses. Subjects will be screened to determine HA titers against the target component (A/Singapore/INFIMH-16-0019/2016 [H3N2]) with the intent to enroll subjects with low titers (≤320 HAI titer).

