6.2.3. Adverse Events

Adverse events will be monitored regularly from informed consent until Visit 05 (28 days after QIV administration). At regular intervals during the study, subjects will be asked non-leading questions to determine the occurrence of any AEs. All AEs reported spontaneously during the study will be recorded as well. Solicited and unsolicited signs and symptoms will be reported as AEs after review by the Investigator or designee, either separately using the corresponding Medical Dictionary for Regulatory Activities (MedDRA) terminology of the sign or symptom or combined using the appropriate term. For example, a subject who reported concurrent cough, runny nose, and sneezing assessed by the Investigator as unrelated to vaccine should have those symptoms grouped as a syndromic diagnosis (URI), with the severity based on the most severe AE/symptom. Therefore, as a secondary presentation, subjects with 3 or more concurrent unrelated AEs of cough, runny nose/rhinorrhea, sneezing, sore throat, itchy throat, itchy eyes, congestion, nasal irritation, hoarseness, headache, body aches/myalgia, tiredness/fatigue, malaise, and fever will have those AEs grouped as URI.

For detailed definitions and reporting procedures of AEs, see Section 9.

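### V05 may fall as early as 21 days after QIV, so AE and SAE collection can stop up to 7 days before the 28-day post-QIV endpoints end

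*Protocol*

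**What the plan says.** The endpoints are defined by elapsed time. Protocol section 2.2.2 counts subjects with "unsolicited AEs during the 28 days after administration of licensed QIV". Section 2.2.1 has two primary endpoints that matter here: "SAEs from the time of informed consent through 28 days after receipt of QIV" and "unsolicited AEs during the 28 days after administration of investigational M2SR vaccine or placebo and prior to administration of licensed QIV".

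The collection period is described in several places, and they do not agree:

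- Protocol 9.1 monitors AEs from consent "until Visit 03 (Day 28 after the IP dose administration) and from Visit 04 until Visit 05 (Day 28 after the QIV dose administration". It adds that "SAEs or medically attended events will be documented from the time of consent until Visit 05".
- Protocol 6.2.3 has no break: "Adverse events will be monitored regularly from informed consent until Visit 05 (28 days after QIV administration".
- Protocol 3.1: "Unsolicited AEs will be recorded from time of consent through 28 days after both M2SR and QIV vaccinations".
- Protocol 8.3: "AEs will be collected for a period of 28 days following the IP and the QIV doses".
- SAP 9.2 records AEs continuously from consent to QIV Day 29.

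The visits that close these periods have two-sided windows: V03 at Day 29 ±3 (Table 2) and V05 at Day 29 ±7 (Table 3). Section 7.1 makes V05 the end of the study. The four-week safety call in section 7.4 is for withdrawn subjects only.

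**The concern.** Sections 6.2.3 and 9.1 both treat V05 as if it were 28 days after QIV. Under Table 3 that is only the target day. A subject seen on the first permitted day has complied with the protocol but leaves with a quarter of the endpoint period unobserved. The SAP does not impute missing data (section 8.4), so in an n (%) table an unobserved stretch reads as no event.

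At the other end, a late V05 lengthens observation. Item d) of the reporting periods in SAP 9.2, events after QIV, states no upper limit on onset.

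No test of AE rates is planned, so the absolute percentages are the safety result. Follow-up that varies by subject goes straight into them.

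**Working it through.** **Convention.** Dosing is Day 1, so elapsed days = study day − 1. The nominal visit gives 29 − 1 = 28 days, which reproduces the protocol's own label for V03 and V05.

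**V05 window (Table 3, Day 29 ±7).**
- Earliest: 29 − 7 = Day 22, or 21 days after QIV. Latest: 29 + 7 = Day 36, or 35 days.
- Shortfall = max(0, 28 − elapsed days). Maximum: 28 − 21 = 7 days, and 7/28 = 25%.
- Maximum excess: 35 − 28 = 7 days.

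**Typical size of the loss.** The documents give no distribution of visit days. Assume they are spread evenly over the 15 permitted days:
- Share seen early: 7/15 = 47%, or 56 of 120 if all subjects reach V05.
- Mean shortfall over all subjects: (1 + 2 + … + 7)/15 = 28/15 = 1.87 days, and 1.87/28 = 6.7%.

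Visits clustered near Day 29 would make both figures smaller.

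**Effect on a reported rate (upper end).** Assume a constant hazard and every V05 on the first permitted day. A true 28-day incidence p is then observed as 1 − (1 − p)^(21/28):

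| True 28-day incidence | Observed by day 21 |
|---|---|
| 5% | 3.8% |
| 10% | 7.6% |
| 20% | 15.4% |

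If events cluster soon after vaccination, the loss is smaller.

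**Does any later contact close the gap?**
- Section 7.1: V05 is the last protocol visit.
- Section 7.4: the call covers withdrawn subjects, not completers.
- Section 9.5: known AEs are followed to resolution, but no contact is scheduled to find new ones.
- SAP 9.2: its QIV Day 29 end point adds no contact.

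**V03 window (Table 2, Day 29 ±3).**
- Earliest: Day 26, or 25 days after IP, which is 3 days short of 28.
- Under an even spread, 3/7 = 43% of separately held V03 visits would be early.
- Footnote 1 to Table 3 lets V03 and V04 be combined only at 28 days or more after V01. SAP 8.2 reports same-day IP Day 29 and QIV Day 1 sampling in about 40% of subjects, so those V03 visits cannot have been early.
- That leaves at most about 0.60 × 43% = 26% of subjects with an early V03.
- Table 3 schedules an AE and SAE check at V04 before QIV is given, and V04 is at least 28 days after IP. An early V03 is therefore not in itself a shortened AE period.

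**The case against.** The strongest reply is that the intent is clear. Sections 3.1 and 8.3 promise 28 days after each dose, SAP 9.2 runs to QIV Day 29, and the SAP takes precedence over the protocol. The target day is 29, and the 25% figure needs a visit on the first permitted day. Windows are the same in both arms, IP is blinded, and no AE comparison is tested.

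Much of this stands. No between-arm bias is built in, and the even-spread figures are only illustrative. Precedence, however, governs analysis and cannot supply observations that no visit collected. The SAP is dated June 2022, after the planned completion in December 2021, and its section 1.1.2.2 uses Day 29 QIV as a label for V05. Whether SAP 9.2 means the calendar day or the visit is therefore open. If it means the calendar day, the overcount from late visits largely disappears. The undercount from early visits remains.

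A reader might also infer that the primary 28-day unsolicited-AE endpoint after IP is cut short in 43% of subjects, by up to 3 of 28 days (11%). The documents do not support that. Section 6.2.3 and SAP 9.2 continue AE collection past V03, and the V04 check comes at 28 days or later. About 40% of subjects could not have had an early V03, and SAEs run without a break to V05 even under section 9.1. SAP 9.2 also already defines treatment-emergent events by start date up to IP Day 29, with later events counted only if judged IP-related.

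The post-IP endpoint is at risk only if section 9.1 is followed literally, or if a subject with an early V03 never reaches V04.

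**Conclusion.** The point holds for V05. For a compliant subject, the post-QIV AE endpoint and the last part of the primary SAE endpoint can miss up to 7 of 28 days (25%, worst case). The 47% share and the 1.9-day (7%) mean loss rest on an assumed even spread of visits. A late V05 can add up to 7 days to the post-QIV count unless QIV Day 29 in SAP 9.2 is read as a calendar day.

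The consequence is unequal follow-up and possible under-counting of absolute rates. It is not evidence of a difference between arms.

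For V03 the finding is narrower. Section 9.1 contradicts section 6.2.3 and SAP 9.2 on AE monitoring between V03 and V04, and the texts need reconciling. They do not show that the post-IP endpoint is generally truncated.

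**What to change.** 1. Reconcile the V05 window with the 28-day endpoints. Either use a window that does not open before QIV Day 29, or keep the window and add a phone AE/SAE contact on or after QIV Day 29 for anyone seen earlier. Section 3.1 already allows phone contacts for AE reporting.
2. Make section 9.1 agree with sections 3.1, 6.2.3 and 8.3 and with SAP 9.2 on one AE collection period, and say explicitly what is recorded between V03 and V04.
3. In SAP 9.2, count only events with onset on or before QIV Day 29 in the 28-day post-QIV endpoint and list later events separately. Report by arm how many subjects had less than 28 days of follow-up after QIV.

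The cost is wording in Table 3, section 9.1 and SAP 9.2, plus slightly tighter V05 scheduling or one short call for early attendees. If collection is already complete, item 3 can still be done and shows the reader how much follow-up was actually lost.

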9.2. Intensity of Adverse Events

All AEs will be assessed by the clinician using the grading system from FDA vaccine toxicity criteria (Appendix 2 for vital signs and systemic AE assessment; Appendix 4 for laboratory AE assessment). For events not included in the protocol-defined grading system, then the following guidelines will be used to quantify intensity.

Mild: events require minimal or no treatment and do not interfere with the subject's daily activities

Moderate: events result in a low level of inconvenience or concern with the therapeutic measures. Moderate events may cause some interference with functioning.

Severe: events interrupt a subject's usual daily activity and may require systemic drug therapy or other treatment. Severe events are usually incapacitating.

Life threatening: any adverse drug experience that places the subject or subject, in the view of the Investigator, at immediate risk of death from the reaction as it occurred, i.e., it does not include a reaction that had it occurred in a more severe form, might have caused death.

Changes in the severity of an AE should be documented to allow an assessment of the duration of the event at each level of intensity to be performed. Adverse events characterized as intermittent require documentation of onset and duration of each episode.

9.3. Causality Assessment

The clinician's assessment of an AE's relationship to test article (vaccine or placebo) is part of the documentation process, but it is not a factor in determining what is or is not reported in the study. If there is any doubt as to whether a clinical observation is an AE, the event should be reported. All AEs must have their relationship to study product assessed using the terms related or not related. In a clinical trial, the study product must always be suspect. To help assess, the following guidelines are used.

Related – There is a reasonable possibility that the study product caused the AE. Reasonable possibility means that there is evidence to suggest a causal relationship between the study product and the AE.

Not Related – The AE is not related to the study product if there is evidence that clearly indicates an alternative explanation. If the subject has not received the study product, the timing of the exposure to the study product and the onset of the AE are not reasonably related in time, or other facts, evidence or arguments exist that strongly suggest an alternative explanation, then the AE is not related.

9.4. Outcome

The outcome of each AE must be rated as follows:

- Recovered/resolved;
- Recovering/resolving;
- Not recovered/not resolved;
- Recovered with sequelae/resolved with sequelae;
- Fatal:
- Unknown.

9.5. Recording of Adverse Events

All (S)AEs occurring during the clinical investigation must be documented in the source documents and eCRF.

Whenever possible, diagnoses should be given when signs and symptoms are due to a common etiology (e.g., cough, runny nose, sneezing, sore throat, and head congestion should be reported as "upper respiratory infection"). Investigators must record their opinion concerning the relationship of the (S)AE to the study drugs in the EDC System. All measures required for (S)AE management must be recorded in the source documents and reported according to Sponsor's instructions.

All AEs occurring at any time during the study (including the in-person follow-up period) will be followed by the Investigator until satisfactory resolution (e.g., value back to baseline value) or stabilization or until final database lock. If necessary, to obtain additional information to ensure safety of the subject, additional blood and urine samples may be taken at the discretion of the Investigator. Certain long-term AEs related to therapy cannot be followed until resolution within the setting of this study. In these cases, follow-up will be the responsibility of the treating physician.

